[name]
[name]

[name]
[name]

Audiobooks for Hearing Loss App as Auditory Training
Small Business Innovation Research (SBIR)
Grant 1R44 DC017403-01A1

NCT04231396

3/23/2021

The research was funded by an SBIR grant 1R44 DC017403-01A1 from the National Institute on Deafness and other Communication Disorders

Minimal Risk Protocol

1) Protocol Title

Audiobooks for Hearing Loss

2) Objectives

The goal of the proposed project is to create an Audiobooks for Hearing Loss (HL) App – an audiobook App that has a wide array of user-selectable features designed to provide auditory training: Help individuals with recent Cochlear Implants/Hearing Aids through the difficult initial adjustment process, and help with transitioning at one's own pace toward the goal of understanding “habitual speech” (speech spoken without special effort to be intelligible). Even if not used for auditory training, this app would provide access to audiobooks where standard audiobooks fail. Thus, the App serves both auditory training and accessibility. Proposed features include enhanced (“clear”) speech modes, visual support by simultaneous display of text and a talking face, and other features that can be enabled or disabled to serve the user's unique needs.

3) Background

Twenty percent or more Americans have a Hearing Loss (HL), a commonly used term that includes congenital deafness as well as aging-related hearing challenges, so severe that it may make communication difficult. Worldwide, this translates into 65 million people with English as a first language.

Hearing aids (HAs) and cochlear implants (CIs) are not enough to remedy this. The types of enhancement these devices can perform is inherently limited due to the requirement that they need to perform their task in real time, since otherwise they would not be lip-synchronized, which is essential in face-to-face communication. For example, they cannot change the temporal structure of incoming speech, even if that may help intelligibility. But there is a deeper shortcoming. When individuals wait too long with obtaining these devices, synaptic and pathway re-organization takes place in the auditory cortex that needs to be addressed, and mere device usage may not be up to this task. Cochlear implants provide a special challenge: Individuals may initially have great difficulty deciphering the unfamiliar sensory input generated by these devices.

There is a growing consensus that HL cannot be addressed with HAs or CIs alone: auditory training is also needed. While face-to-face auditory training is available, this intervention is generally not covered by insurance plans. Auditory training Apps have become available to fill this need in a cost-effective manner. Unfortunately, evidence for the efficacy of these products is weak; a recent large-scale randomized controlled trial found no effect on a wide range of outcome measures. A likely suspect for these results is that most aural rehab Apps are repetitive, even with gamification and rewards. A popular method used by individuals with HL to improve their listening skills is listening to audiobooks. Audiobooks have the strong advantage over many aural rehab Apps of being intrinsically motivating. However, existing audiobooks do not adequately accommodate individuals with more severe levels of HL unless they are fundamentally re-thought.

4) Study Design

We will build an Audiobooks for Hearing Loss App that serves both AT and accessibility. The following features all serve to transform the basic audiobook concept into a powerful tool for AT: (1) Multiple speech modes; (2) Visual supports; (3) Enhanced navigation; (4) Track and train; (5) Usage logging; and (6) Gamification. The App will then be used by individuals with HL, both children and adults with a variety of HL diagnoses using both CIs and HAs. The AT efficacy of the Audiobook for Hearing Loss system will be evaluated from the results of this study.

5) Study Population

a) Number of Subjects

40 subjects will participate in total, including children and adults with HL comprised in 5 distinct HL subgroups.

b) Inclusion and Exclusion Criteria

To establish that the system is widely usable and to examine the AT efficacy of the App we will be comparing five distinct HL subgroups: (1) Adults with HA, moderate HL (41-55 dB HL); (2) Adults with HA, moderately-severe to severe HL 56-90 dB HL); (3) Adults with non-recent traditional CI, post-lingually deaf (4) Children, ages 9+, non-recent-traditional CI, pre-lingually deaf; and (5) Adults and children, ages 9+, recent traditional CI, post-lingually deaf.

These five subgroups span broad ranges in terms of: (1) age (adults vs. children); (2) severity of hearing loss; (3) device used (HAs vs. CIs); (4) familiarity with device (recent vs. longer-term); and (5) onset of HL (pre-lingual vs. post-lingual). The team expects the highest efficacy for children and adults with recent CI who are post-lingually deaf; the lowest efficacy for adults with HA with either moderate or severe HL; and intermediate efficacy for children with non-recent CI who are pre-lingually deaf. While Phase I does not assess AT efficacy of the system, Phase II will, and Phase I needs to establish acceptability of the various aspects of the proposed system for these groups.

Inclusion criteria for all 40 participants will be: speaking English as first language, no suspicions of cognitive deficits or vision impairments that would interfere with system usage or invalidate usability assessment, no signs of external ear disease, being able to read at least a third-grade level and having access to a device that allows them to access a webcam for a video conference call. If participants do not have Bluetooth capability in their hearing aids or CI processors, they will need to be willing to wear either their own headphones or study-provided headphones while using the audiobooks app. All participants will be tested with the Expressive One-Word Picture Vocabulary Test, 4th Edition (EOWPVT-4; Brownell 2000), normed for ages of 2 and older, and are required to score in the 15th percentile or better. Responses to this test, whether correct or incorrect, will also be analyzed for intelligibility. Reading ability will be based on caregiver or teacher reports. Non-traditional/non-standard hearing aids (example: bone anchored hearing aids) or cochlear implants (examples: hybrid or electric acoustic stimulation (EAS)-type) will be excluded.

c) Vulnerable Populations

This study will include children. The inclusion of children is important to the research because the disease being studied affects children, and little is known about the available treatment options in the pediatric population. This study is minimal risk and holds out prospect of direct benefit so one parent/guardian must provide parent permission for the child to be enrolled in

the study. In addition, written permission will be obtained from children who, in the assessment of the investigator, have that capacity. If a child subject reaches the age of majority during the study, he or she will be asked to indicate their willingness for further participation.

d) Setting

The subjects will be seen remotely via video conference call for design, usability, and intelligibility sessions. The Hello clinic is a space that provides speech-language services to children and adults. The subjects will use the Audiobooks for HL App at home and then be seen at their home for weekly sessions by a Researcher.

e) Recruitment Methods

Subjects will be recruited from flyers posted at multiple sources, including local healthcare specialists (Audiologist and Otolaryngologist offices), schools, and hearing loss support group meetings. Most prominently we will be recruiting through the OHSU Institute on Development and Disability (IDD) Rehabilitation Center, and the OHSU Cochlear Implant Division. Individuals will be paid \$20 per session for their participation in the design, usability and intelligibility parts of the study. Individuals will be paid \$80 total for their participation in the evaluation portion of the study. They will receive this payment (up to \$100 total) regardless of whether they complete the study.

Participants will also be identified using the EPIC cohort discovery tool, allowing the study team to identify possibly eligible patients who are seen in the OHSU Cochlear Implant Division and the OHSU Institute on Development and Disability (IDD) Rehabilitation Center. Participants will also be recruited via a Facebook advertisement on the OHSU and OHSU Doernbecher Children's Hospital Facebook Pages. We will rely on OHSU electronic health records to identify eligible individuals who have received a clinical diagnosis of HL based on standard research diagnostic criteria and that they currently wear HAs or CIs.

f) Consent Process

Participants and/or their parent/guardian will receive paper or electronic copies of the appropriate information sheet prior to the first session, to enable them to study the sheet. They will then participate in a telephone or email screening to establish the eligibility of themselves or their child. The telephone or email screen will be performed by OHSU OCTRI personnel that are not involved with either BioSpeech or CSLU. If the participant or parent/guardian is interested then willingness to participate will be obtained verbally over the phone or via video conference call. The information sheet itself as well as any accompanying instructions will make it clear that non-participation has no consequences of any type.

Non-English Speaking Subjects

This study does not involve non-English speaking subjects. Non-English speakers are excluded since the materials will all be English-only. In addition, by excluding participants that have learned English as a second language it will help ensure that any potential language comprehension problems do not interfere with system usage or invalidate usability assessment.

Assent of Children and Parent Permission

One parent/guardian must provide parent permission for the child to be enrolled in the study. In addition, written willingness to participate will be obtained from children who, in the assessment of the investigator, have that capacity. If a child subject reaches the age of maturity during the study, he or she will be asked their willingness for further participation.

6) Procedures

Our study includes a total of 40 participants; 8 individuals from each of these five distinct HL subgroups. The product design/development process (Aim I.2.), usability (Aim I.2.b) and intelligibility (Aim I.3) studies involve one session (N=40). Sessions are expected to take one hour. The evaluation (Aim I.4) requires twelve video sessions. The adult and child groups (N=20 each) are mixtures of the five subgroups that were previous participants. All sessions will be conducted via video conference. Subjects will be sent an iPad with the prototype of the App preloaded.

Participants will start by being administered the Expressive One-Word Vocabulary Test normed for ages 2 and older. Failure to score at least in the 15th percentile will lead to termination of participation, but with full payment of any honoraria. Preceding telephone or email screening will be designed to make such failure extremely unlikely. Special language and procedures will be designed and incorporated in the OHSU IRB information sheet to prevent any negative feelings due to termination.

In the design, usability and intelligibility portions of the study participants will interact with a computerized system, Audiobooks for HL App, in tasks that involve using audiobooks. The researcher will observe and take notes of any problems the subject encounters with the iPad. The subject can take breaks as needed by pausing the screen on the iPad. Then they will answer questions via a survey given by the researcher. This session will take 1- 2 hours and the subject will be paid \$20 regardless of whether the session is completed.

In the evaluation portion of the study participants will be given the BKB-SIN test for the first 6 weeks. Then, the study participants will also use the Audiobooks for HL App for the remaining 6 weeks using the App at least two hours per week total. The researcher will conduct 12 weekly remote visits via video conference where the following will be done:

- Throughout the 12 week study, the BKB-SIN will be administered using 2 new word list pairs in each session rotating through all 18 list pairs. The BKB-SIN is a speech-in-noise test that uses BKB (Bamford-Kowal-Bench) sentences, recorded in four-talker babble.
- During the last 6 weeks of the study the following will be done, in addition to the administration of the BKB-SIN.
- Observe the subject use the audiobook for 20-30 minutes.
- Conduct a comprehension test. Questions will be developed with the Sentence Verification Technique (SVT; Royer, 2001), in which alternative versions of passages in the materials are written and participants are to decide which version matches what was read. These questions (up to 5 per hour of read materials) will be presented in text form and answers will be recorded and scored during the session.
- Address any usability issues the participant brings up.

- Based on discussion with participant (and parent/guardian if available), the usage log, and the comprehension test results: (a) suggest adjusting the speech mode (clear vs. habitual speech, noise level); (b) suggest switching off a visual support (face, synchronized text); discuss next milestone (e.g. completion of a story or book).
- Discuss real-world rewards with parent/guardian if milestones are met.

Throughout the session the researcher will balance emotional support with emphasis that the App is for training, not just for recreation. These individuals will receive an \$80 payment at the end of their 12 weeks regardless of whether they complete the full 12 weeks or not. At the end of 12 weeks, they will be sent instructions and materials to package their iPad device and ship it back with a pre-paid return label.

7) Data

a) Handling of Data

Protected health information including age and HL diagnosis will be collected during the study. Data will be collected using: surveys and an iPad App. The hard copy responses to survey/questionnaires and electronic data (audio, touchscreen responses, test scores, App usage statistics) will be retained for immediate and future analyses. Standard institutional practices will be followed as described by the OHSU Information Security Directives at the following link: <https://www.ohsu.edu/information-technology/information-privacy-and-security> to maintain the confidentiality and security of data collected in this study. Study staff will be trained with regard to these policies.

Paper files with restricted information in transit will be kept out of sight. Once the restricted information has arrived at BioSpeech, it will be secured in a locked filing cabinet. Electronic data will be stored on restricted drives on the OHSU network as well as on the cloud file storage solution provided by Box.com.

Access to data is restricted to study personnel.

Upon enrollment, subjects will be assigned a code that will be used instead of their name, medical record number or other personally identifying information. Electronic files for data analysis will contain only the subject code. Codes will not contain any part of the 18 HIPAA identifiers (initials, DOB, MRN). The key associating the codes and the subject's personally identifying information will be restricted to the PI and the study staff. The key will be kept secure on a restricted OHSU network drive in a limited access folder.

b) Sharing of Results with Subjects

The data will not be shared with the subjects because the research is still in an early phase and the reliability of the results is unknown.

c) Data Banking

All data will be stored for up to ten years for future analyses in this study. Access to data is restricted to study personnel. All of BioSpeech's study personnel are required to participate in a mandatory, ongoing training program on human subject protection. Hard copy data will be secured in a locked filing cabinet. Electronic data will be stored on restricted drives on the OHSU network as well as on the cloud file storage solution provided by Box.com.

8) Data Analysis

We will use a multiple baseline method. We will administer the BKB-SIN in 12 weekly sessions, using 2 new word list pairs in each session rotating through all 18 list pairs. In the training phase, starting in week #7, participants are asked to use the App at least 2 hours per week. To evaluate auditory training efficacy of the App we will measure the change in slope of the curve relating test performance to session number. This will be evaluated by computing for each subject, S , a normalized slope difference, $ZS = (bs_1 - bs_2) / \sqrt{SE_{bs_1}^2 + SE_{bs_2}^2}$; here, $j=1,2$ refers to pre- and in-training phase, and, for each subject S , bs_j 's are the associated slopes and SE_{bs_j} 's the standard errors of the slopes.

The design of the study allows for multiple statistical analyses. We will conduct analysis within-subjects, as noted above. We will also conduct planned comparisons between selected groups, using t -tests, comparing score changes between a pre-post change.

Since ZS is approximately normal, we apply a one-tailed single-sample t -test to the 40 ZS 's, yielding a power of 0.80 at $p=0.05$ (one-tailed) for small-medium effect sizes ($d=0.4$).

9) Privacy, Confidentiality and Data Security

All data will be stored up to ten years. All materials that may have identifying information will be kept secure in a locked filing cabinet. All data will be coded and electronic data will be stored on restricted drives on the OHSU network as well as on the cloud file storage solution provided by Box.com. Any analyses of information will be performed on password-protected computers; no copies will be made. All procedures for HIPAA compliance, where relevant, will be observed. The iPads used for data collection will be password protected. They will not contain any PHI. Specifically, they will not store any information used in the study derived from medical records for determining eligibility and for characterization of the sample, nor performance on the listening tests. Audio recordings will not be identifiable since they will not contain any identifiable information. Access to data is restricted to study personnel.

Coded research records may be reviewed and/or copied by the OHSU Institutional Review Board and the Office for Human Research Protections (OHRP).

10) Risks and Benefits

a) Risks to Subjects

This is a minimal risk study since the procedures involve interacting with user-friendly software and undergoing listening tests and a simple language test (Expressive One-Word Picture Vocabulary Test). Audiobook contents will be carefully selected to be "safe" i.e. age-appropriate for children and non-offensive or fear inducing for adults. These procedures do not contain any elements that are fundamentally different from or riskier than assessments or remediation already received as part of the participant's routine care or intake procedures, or at home, school, or other medical or non-medical environments. Conducting the procedure in an environment familiar to the participant should further reduce any physical or mental discomfort.

There is a risk of time burden the subject may incur from participating in the study. And there is a risk of breach of confidentiality, which is common to almost all research studies.

b) Potential Benefits to Subjects

The key benefit to the subjects is the possibility of improved listening ability. They will be paid \$20 per session for usability/design/intelligibility sessions and \$80 for the 12-week evaluation portion of the study, for a total of \$100 if they participate in both portions. Given the extremely low-risk nature of the study, these benefits outweigh the risks. The information sheet will indicate the purpose of the study.

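### Researcher guidance, milestones and rewards start in the same week as the App, so the slope change estimates the guided App, while section 8 attributes it to the App

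*Combined protocol and SAP*

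**What the plan says.** On the baseline phase, section 6 (Procedures) says: "In the evaluation portion of the study participants will be given the BKB-SIN test for the first 6 weeks". It lists nothing else for those weeks. It then says: "During the last 6 weeks of the study the following will be done, in addition to the administration of the BKB-SIN". The items that follow are 20-30 minutes of observed use, a comprehension test, help with usability problems, advice on speech mode and visual supports based on the usage log and test results, and discussion of the next milestone. The last item is: "Discuss real-world rewards with parent/guardian if milestones are met".

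After this list the section adds: "Throughout the session the researcher will balance emotional support with emphasis that the App is for training, not just for recreation". That sentence names no phase. It presupposes that the App is in use, but the sentence about the last 6 weeks is what fixes the timing.

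Section 6 also provides for 12 weekly video visits, with the BKB-SIN given throughout.

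Section 8 (Data Analysis) fixes the start of App use for everyone: "In the training phase, starting in week #7, participants are asked to use the App at least 2 hours per week". On interpretation it says: "To evaluate auditory training efficacy of the App we will measure the change in slope of the curve relating test performance to session number". For the test it says: "we apply a one-tailed single-sample t -test to the 40 ZS 's". It also plans t-tests of pre-post change between selected groups, without naming the groups.

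Section 4 (Study Design) lists six features of the App, among them usage logging and gamification. Live guidance by a researcher is not one of them, and no section defines it as part of the intervention.

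**The concern.** Two things change at week 7: the participant gets the App, and the visit gains guidance on how to use it, goals to reach and, where a parent or guardian is involved, a discussion of rewards. The analysis has one contrast, before against during training, and assigns all of it to the App.

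This matters for the claim the sponsor wants to make. Section 3 (Background) presents Apps as a cost-effective answer to the lack of insurance cover for face-to-face training, and audiobooks as motivating in themselves. A result obtained with weekly guidance and outside incentives does not show what the App does without them. Guidance need not distort the hearing test for this to hold. It could simply lead to more, or better chosen, App use that an unguided user would not reach.

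The planned group comparisons raise a related point. The rewards step goes through a parent or guardian, so it applies mainly to children.

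**Working it through.** **1. The plan's own figure.** Section 8 gives n = 40, one-tailed alpha 0.05, d = 0.4 and power 0.80. For a one-sample t-test there are 39 degrees of freedom and the noncentrality is d√n = 0.4 × √40 = 2.53. The probability that a noncentral t variable exceeds the one-sided 5% critical value is 0.7997. The stated power is reproduced, so the problem is one of attribution and not of power arithmetic.

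**2. What changes at week 7** (sections 6 and 8).

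| Component | Weeks 1-6 | Weeks 7-12 |
|---|---|---|
| Weekly researcher visit | 6 of 6 | 6 of 6 |
| BKB-SIN | 6 of 6 | 6 of 6 |
| App | 0 of 6 | 6 of 6 |
| Guided use, settings advice, milestones, rewards step | 0 of 6 | 6 of 6 |

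The first two rows are balanced. The last two are identical to each other.

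**3. What the contrast identifies.** Let A be the slope change the App would produce without guidance, and G the further change due to guidance, including any that works through greater App use. Each participant's slope change estimates A + G. The t-test therefore holds its 5% level for the hypothesis A + G = 0, not for A = 0. Because the last two rows of the table never differ, no re-analysis of these data separates A from G. A staggered start would not separate them either, since both would still begin together.

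**4. Which guidance effects reach ZS.** ZS compares slopes fitted within each phase.
- A one-time gain at week 7 that then holds does not alter the in-training slope. Weeks 7-12 have mean 9.5, the deviations are -2.5, -1.5, -0.5, 0.5, 1.5 and 2.5, and these sum to zero, so a constant adds nothing.
- A steady gain over all 12 weeks adds equally to both slopes and cancels.
- Only guidance that changes the rate of improvement within weeks 7-12 relative to weeks 1-6 enters ZS.

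The pre-post t-tests are different: a one-time gain at week 7 would enter those.

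**5. Illustration on assumed values.** The documents give no figure for G. Suppose A = 0 and guidance shifts mean ZS by g standard deviations in the tested direction. The probability of a significant result, by the method of step 1, is:

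| Assumed g | 0 | 0.05 | 0.1 | 0.2 | 0.3 | 0.4 |
|---|---|---|---|---|---|---|
| Probability | 0.05 | 0.09 | 0.15 | 0.34 | 0.59 | 0.80 |

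This shows how the result depends on g. It is not an estimate of g, which could be zero or negative.

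**6. Supervised share of use.** Observed use is 6 × 20-30 minutes = 2-3 hours. Requested use is at least 6 × 2 = 12 hours. If observed time counts toward the minimum, which the plan does not say, it is 2/12 to 3/12, or 17% to 25%, and 75% to 83% is unobserved.

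**7. Groups.** By section 5(b), subgroups 1-3 are adults, subgroup 4 is children and subgroup 5 mixes both. The team expects the highest efficacy in subgroup 5, intermediate efficacy in subgroup 4 and the lowest in adults with hearing aids. A rewards step reaching mainly children falls on the subgroups expected to do better than the hearing-aid adults.

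**8. Could a control arm separate the two?** With 20 per arm, guidance only against App plus guidance, the noncentrality for d = 0.4 is 0.4 × √(20/2) = 1.26 and the one-sided power is 0.34. Power of 0.80 needs 78 per arm, or 2 × 78 = 156 participants against the planned 40.

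**The case against.** The best defence is that most of the added content is delivery of the App. Nobody can observe use, review a log or advise on settings before the App is in use, so its absence from baseline is unavoidable. Section 6 describes the guidance openly, section 4 speaks of evaluating the system, and section 7(b) calls the research early phase. All of this stands, and testing a guided App is a legitimate choice. It does not answer the attribution point, because section 8 names only the App and nothing says the guidance belongs to it.

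A reader might infer more than the documents support:
- *That researcher contact itself starts at week 7.* It does not. There are 12 weekly visits, and only their content changes.
- *That growing effort or rapport would produce a false slope change.* The documents do not say that the BKB-SIN depends on effort, the example milestone is finishing a story or book and not a test score, and step 4 shows that neither a single jump nor a steady rise moves ZS.
- *That the App is meant for unsupervised use because section 2 speaks of the user's own pace.* That phrase describes progress toward understanding ordinary speech, not the absence of guidance.
- *That a child-adult comparison is planned.* Section 8 refers only to selected groups.

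The share of use left unobserved in step 6 also tells against treating supervision as dominant.

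**Conclusion.** The point holds as a limit on the conclusion. The slope change in section 8 estimates the effect of the App with weekly researcher guidance, and by itself it cannot support a claim about the App used without that guidance. The overlap is complete: 6 of 6 training sessions and 0 of 6 baseline sessions, for every participant.

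The size and direction of the guidance contribution cannot be estimated from the documents. The probabilities in step 5 rest wholly on assumed values and do not show that a positive result would be due to guidance. The conclusion assumes that the list in section 6 applies as written, with guidance in the last 6 weeks only. Any group comparison that sets subgroups containing children against adult subgroups carries the rewards step as well.

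**What to change.** In section 8:
- Define the tested intervention as *the App with weekly researcher-guided sessions*.
- Limit the efficacy conclusion to that package.
- State that any planned comparison of subgroups containing children with adult subgroups also includes the parent-mediated rewards step.

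This is a wording change with no added participants, visits or measurements. The cost is a narrower claim: the trial would no longer be said to show what the App does without guidance. Adding researcher conversation to the baseline visits is not a useful alternative. Contact is already balanced, encouragement could itself alter the baseline, and guidance, milestones and rewards would still begin with the App. A guidance-only arm is not practicable at 40 participants, as step 8 shows.

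### Sections 6 and 8 call for 24 new BKB-SIN list pairs where only 18 exist; in full rotation all six repeats fall in the last three training sessions and none in baseline

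*Combined protocol and SAP*

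**What the plan says.** The testing rule appears twice in the combined protocol and SAP. Section 6 (Procedures) says that "the BKB-SIN will be administered using 2 new word list pairs in each session rotating through all 18 list pairs", and section 8 (Data Analysis) repeats it: "We will administer the BKB-SIN in 12 weekly sessions, using 2 new word list pairs in each session rotating through all 18 list pairs".

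The first six weeks are baseline. Section 8 sets the start of the second phase: "In the training phase, starting in week #7, participants are asked to use the App at least 2 hours per week". The outcome is a slope comparison: "To evaluate auditory training efficacy of the App we will measure the change in slope of the curve relating test performance to session number". For each participant the plan divides the difference between the two phase slopes by its standard error (ZS), then applies a one-tailed single-sample t-test to the 40 values, with stated power 0.80 at d = 0.4. It adds a second analysis: "We will also conduct planned comparisons between selected groups, using t -tests, comparing score changes between a pre-post change".

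On sample structure, section 6 says: "Our study includes a total of 40 participants; 8 individuals from each of these five distinct HL subgroups".

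Neither section states the order of the lists, which pairs are reused, whether the order varies between participants, or how repeated lists are handled in the analysis.

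**The concern.** Two pairs at each of 12 sessions is more than 18 pairs can supply without reuse. Staff cannot follow the instruction to the end, and the plan does not say what to do instead.

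Where the reuse falls matters for this endpoint. The comparison is within person, training starts in week 7, and the documents describe no concurrent untrained group and no randomised start of training. Anything that raises scores only late in the training phase therefore cannot be separated from an effect of the App. If people score better on sentences they have heard before, and repeats occur only in the last three training sessions, familiarity with the lists would be counted as training benefit.

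**Working it through.** **Inputs from the documents.** 12 weekly sessions, 2 list pairs per session and 18 pairs (sections 6 and 8); training from week 7, n = 40, one-tailed 0.05, d = 0.4, power 0.80 (section 8); 8 participants in each of 5 subgroups (section 6).

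**1. The plan's own figure.** One-sample t-test with 39 degrees of freedom, noncentrality 0.4 × √40 = 2.53, one-sided 0.05: power 0.7997. The stated 0.80 reproduces. The list count does not enter this calculation.

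**2. List count.** Needed: 12 × 2 = 24. Available: 18. Shortfall: 24 − 18 = 6. Unused pairs last 18 / 2 = 9 sessions.

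**3. Where the repeats fall.** In a full rotation:

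| Sessions | Phase | Pairs (by order of first use) | Status |
|---|---|---|---|
| 1–6 | baseline | 1–12 | all new |
| 7–9 | training | 13–18 | all new |
| 10–12 | training | 1–6 | all repeats, nine weeks after first use |

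So 6 of the 12 training administrations are repeats, against 0 of the 12 in baseline. This holds for every starting point in the cycle.

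**4. Effect on the slope.** Let g be the gain in a session's score when both its pairs are repeats, scored so that higher is better, with the slope difference taken as in-training minus baseline. For six equally spaced sessions the centred times are −2.5, −1.5, −0.5, 0.5, 1.5 and 2.5, so Sxx = 2 × (6.25 + 2.25 + 0.25) = 17.5. A gain in the last three sessions adds

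(0.5 + 1.5 + 2.5)g / 17.5 = 0.257g per session

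to the in-training slope and nothing to the baseline slope. With session residual SD σ, the true standard error of the slope difference is σ√(2/17.5) = 0.338σ, so the shift is 0.257 / 0.338 = 0.76 g/σ standard errors per person.

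**5. Sensitivity range, all on assumed values.** The documents give no g, no learning curve and no σ. The table shows one-sided rejection rates of the ZS t-test with no App effect, by simulation, with n = 40, independent errors and the same g for everyone. Learning follows L(1 − exp(−s/3)) over s = 0 to 11.

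| Assumed learning L | g = 0 | 0.1σ | 0.25σ | 0.5σ |
|---|---|---|---|---|
| none | 0.05 | 0.12 | 0.31 | 0.74 |
| 0.5σ | 0.001 | 0.01 | 0.04 | 0.29 |
| 1.0σ | 0.000 | 0.000 | 0.001 | 0.03 |

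With L = 0.5σ the phase slopes due to learning are 0.0794σ and 0.0107σ, a difference of 0.0687σ against the App. A repeat gain of 0.0687 / 0.2571 = 0.27σ only cancels it.

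**6. Between-group t-tests.** A gain common to all participants cancels. If the pre-post change is a difference of phase means (the plan does not define it), repeats add 3g/6 = g/2 to each person's change, so only half of any between-group difference in g would remain.

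**The case against.** The strongest reply is that rotating through the lists already implies reuse, and that the word for unused lists may mean only that they differ from the previous session's. On that reading the procedure can be carried out and the wording is merely loose. This is fair as far as it goes, but it leaves the repeats in sessions 10 to 12 whenever all 18 pairs are used first. A different order could place them elsewhere, but none is stated, so the placement is conditional and not a fact about the trial.

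The second reply is that no bias is shown. This stands. The repeat gain after nine weeks may be negligible. The largest rates in the sensitivity table need a sizeable gain shared by everyone and no general learning. With learning at the assumed levels, the rate exceeds 0.05 in only one cell.

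The third reply concerns the remedy. Dropping to 18 administrations with no repeats would lower power from 0.80 to about 0.77–0.78 without need. This also stands, and it favours a balanced design that keeps 24 administrations. Under levelling-off learning, moreover, a repeat gain partly offsets the learning bias, so removing it alone can leave the test more conservative. That offset would be accidental and of unknown size, so it is no reason to keep the imbalance.

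**Conclusion.** The conflict between 24 and 18 is certain. Given full use of the 18 pairs before reuse, so is the placement of all six repeats in training sessions 10 to 12. The result is a possible phase-specific confounder of the slope comparison, worth 0.257g per session for a repeat gain g that the documents do not give. Its size, and the net direction once general learning is allowed for, are unknown.

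A reader might infer that the efficacy test is inflated in the App's favour. The documents do not support that: every rejection rate above rests on assumed values, and the table runs from well above 0.05 to well below it. A reader might also infer that the power claim fails. It does not; 0.80 reproduces and does not depend on the number of lists. The planned between-group comparisons are affected only if the repeat gain differs between groups.

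The point should be fixed before testing because the instruction cannot be followed as written and the remedy is cheap.

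**What to change.** In sections 6 and 8, replace the requirement for two new pairs at every session with a reference to a list-allocation table, and add the table:

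- Assign nine of the 18 pairs to weeks 1–6 and the other nine to weeks 7–12.
- Counterbalance which set comes first within each subgroup, four of the eight participants each way.
- Keep two pairs per session, so 12 administrations per phase from nine pairs, with 12 − 9 = 3 repeats in each phase.
- Place those repeats at the same session positions in both phases, for example one in the fifth session and two in the sixth.

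An equal repeat gain then cancels. Each phase slope rises by (1.5 × g/2 + 2.5 × g) / 17.5 = 0.186g, and the difference is zero. If the gain is not the same in both phases, 0.186 times its change remains, and section 8 should state this assumption. In simulation without learning, this layout held the false-positive rate at about 0.05 and power at about 0.80.

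The cost is the table and the wording changes, with no material loss of precision. Repeats now occur within a phase, so at most five weeks after first use instead of nine. The gain may be larger, which makes the matched positions essential.

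The alternative of 18 administrations without repeats removes the equal-gain assumption, at a power of about 0.77–0.78. Neither option addresses general test learning, which needs separate attention.
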